13.4.	Role and Purpose of the Stakeholder Committees	52
13.4.1.	NET-PRO Stakeholder Committees – Membership and Affiliations.....	53
13.5.	Voting at committee meetings	55
13.6.	Attendance at committee meetings	55
13.6.1.	Co-Chairs.....	55
13.6.2.	Members.....	55
13.7.	Resolution of disputes	56
14.	STUDY RESPONSIBILITIES	57
14.1.	Investigator Responsibility/Performance	57
14.2.	Site communications.....	57
14.3.	Study documentation.....	57
14.4.	Protocol Deviations	57

14.5.	Publication policies.....	57
14.5.1.	General guidance for the assignment of authorship:.....	57
15.	PROTECTION OF HUMAN SUBJECTS	58
15.1.	Risk to Human Subjects	58
15.1.1.	Study Procedures, Materials and Potential Risks.....	58
15.1.2.	Adequate Protection against Risks.....	58
15.1.3.	Potential Benefits to Patients	58
15.1.4.	Representativeness of the diversity of the patient population	58
	REFERENCES.....	60
	APPENDIX A: NET diagnosis codes (ICD-9/10), ICD-O-3 codes, and histology codes.....	63
	APPENDIX B: NET Computable Phenotype – technical specification (SAS code).....	66
	APPENDIX C: Pre- and Post-Consent Contacts.....	75

PROTOCOL SYNOPSIS

Neuroendocrine tumors (NETs) are a group of rare and heterogeneous neoplasms which are typically slow-growing in nature. Thus, patients with NETs experience a prolonged clinical course with active disease, with the highest symptom burdens in patients with gastroenteropancreatic (GEP) and bronchopulmonary NETs. However, **assessment of health-related quality of life (HRQoL) and patient reported outcomes (PROs) outside of therapy trials still remains scarce and of poor quality.** What's more, **there are no clear consensus guidelines as to the optimum sequencing of therapeutic options** for NET patients. As clinicians attempt to tailor treatment selection on the characteristics of the patient and their tumor, NET patients must navigate a protracted sequence of treatment decisions as benefits wane and the next modality is tried. **The purpose of this study is to partner with patients to examine the impact of treatment choices on QoL and PROs to achieve the goal of alleviating undue toxicity and optimizing effectiveness and sequencing of therapy for NET patients.**

The Neuroendocrine Tumor – Patient Reported Outcomes (NET-PRO) project is a prospective cohort study of all newly occurring GEP and lung NET cases aged 18 years and older diagnosed between 01/01/2019 and 12/31/2023. Participants will be recruited across 14 participating Patient Centered Outcomes Research Network (PCORnet) sites (from across 4 PCORnet clinical research networks), enrolling an average of 215 patients per site over the 3-year study period (~3,000 patients total), allowing up to a maximum of 60 months of follow-up. Participants will complete four online (or paper) surveys over 18 months; these surveys will focus on patient-reported outcomes, including questions on quality of life, treatment decisions, and experiences with cancer care. These survey data will be linked to individual participant level tumor and clinical characteristics from medical record data.

Project specific aims:

AIM 1: To describe the frequency of treatment regimens and examine their association with symptom burden and PROs and HRQoL outcomes. Enroll a cohort of patients to collect HRQoL and PROs data every 6 months, for 18 months (i.e.: baseline, 6, 12 and 18 month follow-up surveys). We will determine what combinations of therapy are being used, and the changes in symptoms, PROs and HRQoL associated with these different therapeutic choices.

AIM 2: To examine the association of patient, clinical, and tumor characteristics on treatment choice. We will use EMR data to investigate the impact of pre-existing comorbidities (i.e.: cardiovascular, renal and liver disease and diabetes), prognostic tumor factors (derived from cancer registry data) i.e.: stage, grade and nodal status, on the selection of therapies received and outcomes of survival and disease progression (collected via targeted chart reviews).

AIM 3: To compare the effectiveness of peptide receptor radionuclide therapy (PRRT) regimens on outcomes of renal toxicity, disease progression, and patient symptoms and HRQoL. We will utilize the combined PROs gathered in aim 1 and EMR data mined in aim 2 (i.e.: predictors), to compare the effectiveness of various PRRT treatment combinations and sequences, on outcomes of reduced creatinine clearance (renal toxicity), HRQoL and symptom burden, and survival and disease progression. We will further study the heterogeneity of these treatment effects by grade of differentiation (G1/2 vs G3) and NET subsite (GEP vs lung).

AIM 4: To develop and leverage PCORnet infrastructure for the study of NETs and other rare diseases, and to disseminate lessons learned. Finally, we plan to share the infrastructure this study will generate (i.e.: electronic identification of NET patients, entry and completion of tumor table data in PCORnet, and a unique NET personal health record research portal), to foster future studies in NETs and other rare

diseases utilizing the PCORnet data resource, and expand our prospective enrollment through our four nationally representative partnering patient advocate organizations.

1. INTRODUCTION

1.1. Background

NETs are a group of rare and heterogeneous neoplasms that originate in specialized neuroendocrine cells, predominantly in the small bowel, pancreas and lung, collectively affecting fewer than 172,000 individuals in the United States [1]. Although NETs may arise in most organs, more than half originate from endocrine cells of the gastrointestinal tract and the pancreas [2], referred to as gastroenteropancreatic NETs (GEP-NETs). Both GEP-NETs and lung NETs, including typical and atypical carcinoid tumors and bronchial NETs, meet the criteria for orphan disease status. Despite this, the age-adjusted incidence rate of NETs increased 6.4-fold from 1973 (1.09 per 100 000) to 2012 (6.98 per 100 000) [3, 4], and serves only to highlight the growing impact and burden these cancers will continue to have on the health of our population.

1.1.1. Health related quality of life impact of NETs

NETs are typically slow-growing in nature with prolonged survival and significant symptom burdens, however few studies have examined quality of life impacts. Their vague antecedent signs and symptoms cause significant delay and difficulty in their diagnosis and detection [3]. Metastatic disease is observed in up to 40% of NETs at initial diagnosis [1], and many patients with liver or other distant metastases experience carcinoid syndrome, a direct result of the tumors capacity to synthesize and secrete an excess of bioactive amines, peptides, and polypeptides. Carcinoid syndrome manifests with clinical symptoms ranging from watery diarrhea and flushing to bronchospasm, to hypotension and right-sided cardiac deficits (carcinoid heart disease) due to serotonin hypersecretion [4]. In fact, a Surveillance Epidemiology and End Results (SEER) analysis has shown that 19% of all NET patients have symptoms of carcinoid syndrome at diagnosis, increasing to over 50% in patients with metastatic well-differentiated small bowel NETs [5]. Thus, NET patients typically experience prolonged survival with active disease, and many have significant symptom burdens. With a conscious shift in medical practice from disease-centered to patient-orientated care, quality of life represents an important measure for gauging patient perspectives on treatment effectiveness and outcomes. However, the assessment of health-related quality of life (HRQoL) in NET patients is relatively infrequent and transfer of HRQoL results into clinical practice is hindered by the often limited quality of HRQoL outcomes reporting [6]. Unsurprisingly, where these studies have been undertaken, some have identified worse HRQoL scores in NET patients as compared with the general population [7-10], specifically poorer patient-reported outcomes and unmet needs [11, 12]. In fact, a high prevalence of moderate to severe symptoms especially tiredness (44-50%), lack of well-being (37-49%) and anxiety (30-40%), have been observed up to five years after diagnosis, with the highest symptom burdens in patients with bronchopulmonary and GEP-NETs [13].

1.1.2. Nomenclature of NETs

The complex and confusing nomenclature of NETs contributes to a thin evidence base for optimal management. This is very unfortunate as tumor differentiation and tumor proliferation are important indications of underlying tumor biology, carrying predictive, prognostic, and therapeutic significance. In 2010 the World Health Organization (WHO) introduced a common framework for the classification of NETs [14], morphologically dichotomizing the tumors into well differentiated NETs, and poorly differentiated neuroendocrine carcinomas (NECs) on the basis of the tumor's mitotic rate and Ki67 index [15]. However, this dichotomous grading criteria is imperfect, and a new subset of well-differentiated grade 3 NETs (predominantly in the pancreas, stomach and colon) has since been recognized, with a

worse prognosis than G2 NETs, and non-standardized treatments straddling G1/2 tumors and poorer prognosis NECs [16] (Figure 1).

WHO 2017	Mitoses/10 HPF*	Ki-67 Index*
Well-differentiated NENs		
NET grade 1	< 2	< 3
NET grade 2	2–20	3–20
NET grade 3	> 20	> 20
Poorly differentiated NENs		
NEC grade 3	> 20	> 20
Small-cell type		
Large-cell type		
MiNEN*		

HPF = high power fields, MiNEN = mixed endocrine non-endocrine neoplasm, NEC = neuroendocrine carcinoma, NET = neuroendocrine tumor, WHO = World Health Organization

*Mitotic count counted in 10 HPF. 10 HPF=2mm². Cut-offs per American Joint Commission on Cancer Staging Manual, 7th ed.

*Ki-67 index: percent positive after count of 2000 cells in area of highest nuclear labelling. Cut-offs per American Joint Commission on Cancer Staging Manual, 7th Ed.

Figure 1: WHO 2017 GEP-NET nomenclature and classification

1.1.3. Gaps in Optimal therapy selection and sequencing

Figure 2 presents an algorithmic overview of the investigation and treatment of GEP-NETs (the most common NET subtype) [17]. For low to intermediate grade NETs, surgery remains the mainstay of treatment and the requirement for adjuvant therapy is questionable [18-20]. However, as over half of GEP-NETs present with metastases at the time of diagnosis, they are not considered candidates for curative surgery, and so many are offered some form of long-term medical treatment for symptom relief and tumor growth suppression. Somatostatin analogues (SSAs) are established first-line agents for low-grade GEP-NETs, largely given their demonstrated improvements in overall survival in two placebo-controlled randomized trials ([PROMID](#) and [CLARINET](#)) [21, 22]. However, there are no clear consensus guidelines as to the optimum sequencing of other therapeutic options [17, 21, 23-27]. Systemic, non-liver directed therapies may include peptide receptor radionuclide therapy (PRRT), interferon alpha, everolimus (an mTOR inhibitor), sunitinib (a tyrosine kinase inhibitor), bevacizumab and cytotoxic agents [17]. Liver-directed therapies include ablative therapy, transarterial embolization and chemoembolization, and internal radiation therapy with yttrium-90 coated microspheres [28]. Interestingly, an assessment of the clinical benefit of systemic treatments in GEP-NETs found that currently used treatments had low health benefit scores according to the ASCO-NHB, and none could be graded as meaningfully clinically beneficial according to the ESMO-MCBS [29]. Therefore, one of the greatest challenges in the current NET oncology management landscape is how best to sequence these many therapeutic options (if warranted at all), and how to tailor treatment selection on the basis of the individual characteristics of the tumor and patient.

PRRT represents a true breakthrough in treatment of NETs but many questions remain about sequencing of PRRT with other therapies. PRRT is a form of molecularly targeted therapy, the main goal of which is to selectively deliver a high dose of radiation to the tumor cells, thus limiting irradiation of normal tissues. Unfortunately, due to tubular reabsorption and intracellular trapping of the radionuclide, PRRT therapies can accumulate in the renal cortex inducing toxicity [30]. Proper kidney protection, with the co-infusion of positively charged amino acids, is mandatory. Whilst the radiation dose to the kidneys can be reduced with this pre-treatment, the kidney remains a dose limiting organ

[31] with a creatinine clearance loss of about 3.8% per year for ¹⁷⁷Lu-octreotate and 7.3% per year for ⁹⁰Y-DOTATOC [32]. Moreover, studies have demonstrated a higher and more persistent decline in creatinine clearance if risk factors for delayed renal toxicity are present, particularly long-standing and poorly controlled diabetes and hypertension [33, 34]. On January 26, 2018, the US Food and Drug Administration (FDA) approved Lutathera (¹⁷⁷Lu-DOTATATE), a radiolabeled somatostatin analog, for the treatment of adults with somatostatin receptor-positive GEP-NETs [35]. Lutathera, is the first radiopharmaceutical to be approved by the FDA for this patient population. We are likely to see an increase in the use of ¹⁷⁷Lu-DOTATATE outside specialist NET centers. Therefore, real-world data on variables that may influence patient reported outcomes (i.e.: toxicities and adverse effects) and risk of progression after PRRT in combination with other biological therapies, is much needed.

Optimal sequencing of therapy is a key concern for most patients. As NETs are relatively slow-growing, even patients with metastatic disease can be expected to be treated for protracted periods of time, and must navigate a prolonged sequence of treatment decisions as benefits wane and the next modality is tried [26]. NET patients have been left wondering not only ‘what therapy would be best to try next?’, but ‘if I were to take this option now, what treatment options will be closed off to me in the future?’ (personal communication, [name], lead patient advocate Co-I). As numerous toxicities may result from these therapies including hematologic [36-38], renal [27], and hepatotoxicity [39], patients may run out of resilience to withstand toxicity before they run out of therapeutic options. This real concern was underscored in a recent network meta-analysis of 30 randomized trials finding severe and life-threatening adverse effects ranged from 3.0% to 83.9% depending on the treatment combinations utilized [40], underlining the importance of mitigating toxicity and optimizing sequencing of therapy for patients with prolonged survival.

[figure not shown]

Figure 2: Overview of treatment for GEP-NETs

SSA: Somatostatin Analogues, PRRT: Peptide receptor radionuclide therapy, 5FU: 5-fluorouracil, STZ: Streptozocin-based chemotherapy, CAPTEM: capecitabine with temozolomide, SRI: somatostatin receptor imaging, TAE: Trans-arterial embolization, TACE: Trans-arterial chemoembolization, CS: refractory carcinoid syndrome, RFA: radiofrequency ablation.

1.1.4. Important NET subgroups

Metastatic well-differentiated grade 3 NETs are a challenging and heterogeneous subgroup. Predominantly localized to the pancreas, stomach and colon the prognosis of these tumors is poorer than grade 2 NETs. Current European and American guidelines recommend surgical resection for localized disease (irrespective of grade), but chemotherapy is indicated in grade 3 NETs, particularly if it would enable a surgical procedure [16]. Researchers from the University of Iowa [41] and Vanderbilt ([name], Co-I), two large dedicated multidisciplinary NET clinics, are showing that earlier utilization of PRRT (neo-adjuvantly) in these patients may improve patient outcomes (progression-free survival), indicating that there may be other treatment sequences and combinations in this subgroup of equal or greater effectiveness, and with potentially reduced long-term toxicities.

There are currently several ongoing NET phase III clinical trials. [NETTER 2](#) examines Lutathera (177-Lu DOTATATE) in comparison to high dose SSA in higher G2 and low G3 GEP-NET patients. [COMPETE](#) compares Lu177-DOTATOC with everolimus treatment in G1/G2 GEP-NET patients. The [CABINET](#) trial is comparing use of a tyrosine kinase inhibitor vs placebo in a variety of NET patients previously treated with everolimus. Further, a more recent phase III trial [COMPOSE](#) (not yet recruiting), will evaluate the efficacy, safety & patient-reported outcomes of 177Lu-Edotreotide to best standard of care options (including chemotherapy and everolimus) in G2/G3 GEP-NETs. Importantly however, these trials will take several more years to report results and will enroll fewer than 400 patients each. Moreover, there is a marked disservice in these clinical trials to patients with lung NETs. In fact, typical and atypical carcinoids (low-grade NETs of the lung and bronchus) are neglected diseases in respect to both high-grade NETs of the lung (i.e.: small-cell lung cancer and large-cell neuroendocrine carcinoma) and GEP-NETs, with therapeutic options often extrapolated from studies undertaken in patients with GEP-NETs [42]. The conduct of a comparative effectiveness research (CER) study in the setting of typical and atypical carcinoids is particularly warranted.

1.1.5. Significance

The lack of consensus guidelines as to the optimum sequencing of treatments, means that NET patients and clinicians are confronted with very real and difficult treatment decisions. Due to the relatively small number of patients included in clinical trials related to the important NET subgroups previously highlighted, it is difficult to evaluate both the factors that may affect treatment receipt and their influence on patient-reported outcomes and prognosis. Our large study's rigorous collection of symptom, tumor and treatment burdens and their impacts on HRQoL indicators will improve patient outcomes through the application of more informed treatment sequencing and monitoring of disease burden. While patients with a localized, resectable tumor may go straight to surgery, those with locally advanced or synchronous metastatic disease may benefit from the delivery of a more complicated series of treatments which are somewhat personalized to the preference of the patient and the proliferative profile of their tumor.

The NET-PRO study will address at least three large challenges patients face in what they are offered for the current management of NETs.

- a. Unknown optimal sequencing of systemic and non-systemic therapeutic options. Because clinicians currently do not understand what options (with the lowest toxicities) should be tried first given a patient's particular proliferative tumor burden, they are not able to provide evidence-based recommendations. Our communications with NET patients and our patient advocacy partners strongly attest that this is a research question that is important to them. This is what is driving our study aim 3, which will compare the effectiveness of various PPRT treatment combinations and sequences on outcomes of renal toxicity and radiographic evidence

of disease progression. This prospective CER study may ultimately help improve the standardization and optimization of PRRT procedures [43], increasing therapy effectiveness, driving adoption of protective interventions, and improving patient outcomes.

- b. Treatment of grade 3 well differentiated NETs is an area of controversy. Data from two of our participating sites (Iowa and Vanderbilt) is supportive of earlier initiation of PRRT in these patients (neo-adjuvant setting), and a large CER study with targeted chart review and electronic medical record (EMR) data would be able to assess progression-free survival outcomes.
- c. Lung NETs are an underserved NET cohort currently prescribed the same treatment/management practices as GEP-NETs, even though they are recognized as a specific entity; the lower frequency of these tumors at single academic medical institutions precludes robust investigation and inclusion in randomized trials. CER studies in lung NETs are therefore particularly appealing in this often neglected population.

1.1.6. Potential to advance rare disease research using PCORnet

There is currently no large nationally recruiting prospective study of NET patients. The PCORnet resource is the ideal platform to evaluate in large patient numbers, real-world CER questions on the disease burden and treatment effects and toxicities that matter most to NET patients, their caregivers, and clinicians involved in their care. We expect that the lessons learned by partnering with patients to design the interactive NET patient health record (PHR) portal will yield generalizable knowledge about the information needs for other rare disease populations.

2. SPECIFIC AIMS

The aims of this project will be addressed through the conduct of a prospective cohort study. The general approach to the creation and workflow of this cohort (in reference to the study specific aims) are briefly outlined below.

2.1. Purpose

The purpose of this project is to partner with patients on CER to achieve the goal of mitigating toxicity and optimizing effectiveness and sequencing of therapy for patients with NETs.

In order to achieve this overall goal, we have four specific aims. Aim 1 addresses the patient question of ‘what therapy would be best to try next?’ in the context of symptom burden and quality of life. Aim 2 addresses patient concerns surrounding the question of ‘If I were to take this option now, what treatment options will be closed off to me in the future’, by examining patient and tumor factors associated with overall survival and disease progression. Aim 3 leverages the data obtained in aims 1 and 2 to inform a comparative effectiveness study of contemporary concern, with a focus on patient-centered quality of life and toxicity outcomes. Aim 4 will aid dissemination of our study results and contribute to PCORnet rare disease infrastructure.

AIM1: To describe the frequency of treatment regimens received by line of therapy, and examine their association with symptom burden and changes in 6, 12 and 18 month HRQoL outcomes. The influence of patient preferences, beliefs, attitudes, and experience of care on choice of these treatment regimens will also be examined.

Expected outcomes of aim 1: This aim will enable the ascertainment of patient-reported outcomes (PROs) related to the experience of symptom burden and toxicities for various therapies (and combination treatments) and explore the patient’s attitudes and beliefs that impact the choice of treatment sequencing beyond the basis of clinical and tumor characteristics. Descriptive analyses of these important PROs (that do not exist in the patient’s EMR will determine what combinations of therapy are being used, and the changes in symptoms and HRQoL associated with these therapeutic choices.

AIM 2: To examine the association of patient, clinical, and tumor characteristics on the selection of first-line and beyond treatment regimens and compare the effects of common treatment sequences on frequency of subsequent treatments received and outcomes of overall survival and disease progression.

Expected outcomes of aim 2: This aim will collect existing EMR data among the patients identified in aim 1. We will investigate the patients’ pre-existing comorbidities (i.e.: cardiovascular, renal and liver disease and diabetes), prognostic tumor factors (derived from the population of PCORnet cancer registry tumor data tables i.e.: stage, grade nodal status, mitotic count and Ki-67 index) and the effect of these on the selection of multiple line therapies received. We will additionally examine the effect of these patient, clinical and tumor factors on outcomes pulled via targeted chart reviews i.e.: disease progression and overall survival.

AIM 3: To compare the effectiveness of PRRT regimens on outcomes of renal toxicity, disease progression, and patient-reported symptoms and HRQoL.

Expected outcomes of aim 3: We will complete a comparative effectiveness study of PRRT with or without administration of other systemic therapies (e.g.: everolimus). We will utilize the combined PRO’s gathered in aim 1 and EMR data mined in aim 2 (i.e.: predictors), to compare the effectiveness of various PRRT treatment combinations and sequences, on outcomes of reduced creatinine clearance (renal toxicity) and HRQoL and symptom burden. We will additionally examine the effect on disease

progression of embolization therapy and chemotherapy prior to/following PRRT. Exploring the effectiveness of these outcomes in grade 3 well differentiated NETs and lung NETs (current areas of controversy and under study respectively) will be greatly beneficial.

AIM 4: To disseminate lessons learned and expand enrollment of the prospective cohort to other interested PCORnet sites, patient advocate organizations, and to use the infrastructure developed to aid in the study of other rare diseases.

Expected outcomes of aim 4: By collaborating with several key national NET patient advocacy organizations, and by fulfilling our stakeholder engagement plan, we will fashion a robust and early dissemination plan distributing findings to NET patients before the close of the study. Partnering with 14 participating sites from 4 PCORnet clinical research networks (CRNs) and their institutional media outlets, we will share results that are customized to local settings of care. The NET patient phenotype, tumor table data quality curation scripts, and NET patient health record (NET PHR) portal infrastructure this study will generate, will be loaded to open-source tool-sharing sites and to the PCORnet Commons. These tools will be useful for fostering other CER studies in NETs and could easily be re-purposed for applications in other rare diseases. Finally, we expect to submit grants to conduct new studies with this infrastructure, including following more patients for longer-term outcomes of this indolent disease. If our NET PHR portal is found to offer value to patients, we expect to maintain it as part of this ongoing research.

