4. STUDY DESIGN

4.1. Time anchors for study cohort

Study Period: 01/01/2019 to 12/31/2023 (5 years, max 60 months follow-up)

Index Date: Date of diagnosis of eligible NET tumor in the study period

Source Data Range: 01/01/2017-12/31/2023 (7 years, includes 2-year look-back period)

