- 2) **European Organization for Research and Treatment of Cancer - Quality of Life Questionnaire - Neuroendocrine Carcinoid Module (EORTC QLQ-GI.NET21)** The EORTC QLQ-C30 can be used in conjunction with the EORTC QLQ-GI.NET21 specific questionnaire, which comprises a total of 21 items: four single-item assessments relating to muscle and/or bone pain (MBP), body image (BI), information (INF) and sexual functioning (SX), together with 17 items organized into five proposed scales: endocrine symptoms (ED; three items), GI symptoms (GI; five items), treatment-related symptoms (TR; three items), social functioning (SF21; three items) and disease-related worries (DRW; three items). Responses to the QLQ-GINET21 will be linearly transformed to a 0-100 scale using EORTC guidelines, with higher scores reflecting more severe symptoms.

[Time Frame: Change in mean score across baseline, 6, 12, and 18 month time points.]

- 3) **Sequencing of treatment regimens from electronic medical records.** This will involve identifying which treatments a patient used during their follow-up, and also in what order they received treatment. Dates and types of therapy initiated will be pulled from each patients EMR in reference to the patient’s index date (date of diagnosis). We will also be asking patients about their treatments (self-reported) in the baseline survey to ascertain potential missed therapies in the EMR. We will be comparing the frequency (N) and proportion (%) of use of a variety of therapies (i.e.: SSAs, bevacizumab, cytotoxic chemotherapy, everolimus, Interferon alpha, embolization, PRRT, small molecule TKIs) and the effects of their ordering/sequencing on outcomes of symptom burden and HRQoL.

[Time Frame: Up to 5 years, baseline to end of follow-up]

- 4) **Renal function.** Glomerular filtration rate (GFR) is the best overall index of kidney function. Normal GFR declines with age, and varies according to sex, race and body size. We will calculate creatinine clearance loss [54] by combining individual level CDM and enrollment questionnaire data on sex, race, height, weight and serum creatinine mg/dl laboratory values at regular intervals before and after PRRT cycles until the end of follow-up.

[Time Frame: Change in eGFR from baseline to end of follow-up.]

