9. STATISTICAL ANALYSIS PLAN

9.1. General Statistical Approach

Continuous variables will be summarized using descriptive statistics such as mean, standard deviation, median, minimum and maximum. Categorical variables will be summarized by count and percentage. Group comparisons will be assessed using chi-squared or Fisher's exact tests for categorical variables, and an analysis of variance or Kruskal-Wallis tests for continuous variables where appropriate. Adjustment for covariates listed in Tables 2 and 3 will be explored for each analysis as needed to account for potential confounding effects. Time-dependent covariates will be incorporated to capture changes in covariates across time, as necessary. Inclusion of random effects to account for potential clustering of patients treated at the same study site will be explored. Depending on the rate and pattern of missing data, multiple imputation methods may be considered to account for data missing at random or attributable to non-ignorable drop-out [56]. Planned study outcomes are summarized in Table 4.

9.1.1. Aim 1

Mixed effects regression models will be utilized to assess changes in HRQoL and symptoms within and between groups (i.e.: different treatment regimens) over time. Random effects will be employed to account for the longitudinally correlated nature of repeated questionnaire measurements. Should completion of questionnaires deviate from the planned assessment time points, a spatial power covariance structure will be included to account for the unequal time spacing between assessments within a patient.

9.1.2. Aim 2

Multinomial logistic regression models will be used to identify which patient, clinical, and tumor characteristics (Table 2), and patient attitudes and beliefs (Table 3) influence selection of treatment regimens for each line of treatment. The conditional Cox regression model proposed by Prentice, Williams, and Peterson (PWP) will be used to simultaneously model the gap times between initial diagnosis and first progression and between subsequent progressions as a function of the prognostic factors of interest for progression-free survival. The baseline hazard is expected to differ for first-line therapy and for subsequent lines of therapy, thus event-specific estimates will be obtained. A robust sandwich estimator will be used to account for potential dependencies within patients. Overall survival will be evaluated using a Cox regression model.

9.1.3. Aim 3

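### Aim 2's comparison of sequences on how often later treatments are given has no at-risk denominator and no handling of death, so it cannot by itself show that options were closed off

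*Protocol*

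**What the plan says.** Protocol section 2.1 links Aim 2 to the patient's question about "what treatment options will be closed off to me in the future". It says the aim addresses that question "by examining patient and tumor factors associated with overall survival and disease progression". The formal Aim 2 statement goes further and undertakes to "compare the effects of common treatment sequences on frequency of subsequent treatments received and outcomes of overall survival and disease progression".

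The Aim 2 primary outcome in Table 4 is the sequencing of regimens. Section 7.1, item 3, describes it: "This will involve identifying which treatments a patient used during their follow-up, and also in what order they received treatment". The stated summary is "comparing the frequency (N) and proportion (%) of use of a variety of therapies".

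Section 4.1 fixes a calendar end to observation: "Study Period: 01/01/2019 to 12/31/2023 (5 years, max 60 months follow-up". Patients diagnosed later are therefore watched for less time.

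Section 9.1.2 names three analyses for Aim 2:
- multinomial logistic models for the characteristics that "influence selection of treatment regimens for each line of treatment";
- a Prentice-Williams-Peterson gap-time model for progressions;
- a Cox model for overall survival.

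None is assigned to the later-treatment outcome. Section 9.2.2 calls the Aim 2 analyses exploratory.

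**The concern.** Of the three outcomes in the Aim 2 statement, only the frequency of later treatments describes what a patient went on to receive. A reader will naturally look to it for evidence on options lost.

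Three quite different patients have no later treatment on record at the cut-off:
- one whose disease is still controlled and who needs nothing more;
- one who progressed and received nothing;
- one who died before a further line.

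The second, and arguably the third, bear on options being lost. The first is a success. A proportion taken over everyone followed, for whatever time each was followed, does not tell them apart. A difference between sequences on that proportion could reflect duration of control, early death, length of observation or true loss of options.

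**Working it through.** **Inputs.** From section 9.2.2 and Table 6: median PFS pairs of 12 v 24 and 24 v 36 months; 48 months of uniform accrual plus 12 months of follow-up, so 12 to 60 months of observation; 1:1 allocation; no loss; two-sided 5% log-rank test. The protocol describes these scenarios as purely hypothetical. Exponential times are assumed here.

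**Step 1: reproduce Table 6.** With λ = ln 2 / median, the share with an event by the cut-off is

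P = 1 − (e^(−12λ) − e^(−60λ)) / (48λ).

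- Median 12: 1 − (0.5000 − 0.0313)/2.7726 = 0.831
- Median 24: 1 − (0.7071 − 0.1768)/1.3863 = 0.617
- Median 36: 1 − (0.7937 − 0.3150)/0.9242 = 0.482

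Expected events for 45 per arm, 12 v 24 months, are 45 × (0.831 + 0.617) = 65.2. A Lakatos-type log-rank integration gives:

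| Medians (months) | n per arm | Table 6 power | Recomputed |
|---|---|---|---|
| 12 v 24 | 45 | 0.79 | 0.795 |
| 12 v 24 | 50 | 0.83 | 0.835 |
| 24 v 36 | 175 | 0.80 | 0.801 |
| 24 v 36 | 190 | 0.83 | 0.832 |

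Table 6 is reproduced, so the exponential model is a fair reading of its design.

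**Step 2: duration of control alone.** Treat every PFS event as a progression, let every progressing patient start a next therapy, and allow no deaths first. No option is closed off by either regimen. The crude share with a later treatment is then P itself:
- 12 v 24 months: 83.1% v 61.7%, about 21 points lower for the longer-control regimen;
- 24 v 36 months: 61.7% v 48.2%, 13.5 points lower.

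The remaining 16.9%, 38.3% and 51.8% are simply still controlled. If observation ran uniformly from 0 to 60 months instead, P = 1 − (1 − e^(−60λ))/(60λ) gives 72.0%, 52.5% and 40.7%, so gaps of 19.5 and 11.8 points.

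**Step 3: vary the assumptions** (simulation, 1,000,000 patients per setting, Table 6 follow-up). Let q be the chance of a next therapy after progression, equal in both regimens, with equal death before progression.

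| q | Median time to death | Median 12 | Median 24 | Median 36 |
|---|---|---|---|---|
| 1.0 | none | 83.1% | 61.8% | 48.1% |
| 1.0 | 60 months | 72.9% | 52.1% | 39.9% |
| 0.8 | none | 66.5% | 49.4% | 38.6% |
| 0.6 | 60 months | 43.6% | 31.2% | 23.9% |

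The longer-control regimen is lower in every equal-death setting run. The 12 v 24 month gap is about 12 to 21 points. Among patients who progressed, the share treated equals q for all three medians, as it should.

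**Step 4: a real difference can be reversed.** Suppose the 12-month regimen leaves 80% of progressing patients able to get a next therapy and the 24-month regimen leaves 100%. The crude figures are 66.5% v 61.8%, so the regimen that closes off nothing looks worse.

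**Step 5: unequal deaths.** Fix q = 0.8 and give the 24-month regimen a median time to death of 120 months: 45% receive a later treatment. For the 12-month regimen the share is 62% if its median time to death is also 120 months, 49% at 24 months, 45% at 18 months and 38% at 12 months. The gap shrinks, vanishes and then reverses.

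**The case against.** The strongest reply is that the protocol never says closure of options is judged by this frequency. Section 2.1 ties that question to factors associated with survival and progression. Both are outcomes in the same Aim 2 sentence, both have models in section 9.1.2, and section 9.2.2 gives PFS as the aim's primary objective. Early death and longer control would therefore show elsewhere in the results. This stands. A reader might infer that Aim 2 rests its answer on the frequency, but the text does not support that.

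A reader might also infer that controlled and dead patients are all scored as zero, or that the multinomial models have no category for receiving nothing. Neither is written. No scoring rule, denominator or list of categories is given, and an analysis plan not shown could settle each of them. Section 9.3 says the plan will be refined.

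Finally, a reader might infer that the longer-control regimen must look worse. Step 5 shows that this depends on deaths before a further line being similar.

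What the reply does not remove is that sequences are to be compared on this outcome and that the only summary described is a count and percentage over follow-up. Survival and progression reported separately do not turn that percentage into a measure of access to later therapy. The time-dependent variables in section 9.3 act within regression models and supply no at-risk denominator here.

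**Conclusion.** The point holds in a limited form. As described, the frequency of later treatments mixes continued control, progression without further therapy, and death, under unequal follow-up. It cannot by itself show that options were closed off, and it can mislead.

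On Table 6's own design the artefact is about 21 points (12 v 24 months) and 13.5 points (24 v 36 months). This assumes exponential times, that every PFS event is a progression followed by a next therapy, and that nobody dies first. Section 7.2 counts death as a PFS event, so those figures are illustrations, not forecasts. The receipt and death rates in Steps 3 to 5 are assumptions too. The direction is fixed only when deaths are similar.

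Because Aim 2 is exploratory and reports survival and progression alongside, this is a worthwhile improvement to one comparison. It does not undermine the aim.

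**What to change.** In sections 2.1 and 9.1.2, replace the crude frequency with:
- the cumulative incidence of starting a next therapy, by type, from the start of the index regimen, with death without a next therapy as a competing event;
- the share still progression-free, reported beside it;
- among patients with recorded progression, the share receiving each next therapy, with no further therapy as an explicit category.

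The data are already planned: therapy dates (section 7.1), the four-level disease status that separates progression with and without a treatment change (section 6.2), and death dates (section 7.2). The cost is a change of wording and some extra analysis. The share among progressing patients must be presented as descriptive, because reaching progression depends on the earlier regimen.
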